16.1 Quality Assurance

Eligibility of patients will be verified with the Principal Investigator. Only the designated investigators can obtain informed consent.

There are several different mechanisms by which clinical trials are monitored for data, safety and quality. There are institutional processes in place for quality assurance (e.g., protocol monitoring, compliance and data verification audits, therapeutic response, and staff education on clinical research QA) and departmental procedures for quality control, plus there are two institutional committees that are responsible for monitoring the activities of our clinical trials programs. The committees: *Data and Safety Monitoring Committee (DSMC)* for Phase I and II clinical trials, and the *Data and Safety Monitoring Board (DSMB)* for Phase III clinical trials, report to the Center's Research Council and Institutional Review Board (see section 16.2).

During the protocol development and review process, each protocol will be assessed for the level of risk and the degree of required monitoring. Every type of protocol (e.g., NIH sponsored, in-house sponsored, industrial sponsored, NCI cooperative group, etc.) is reviewed and monitoring procedures are established at the time of protocol activation.

16.2 Data and Safety Monitoring

The Data and Safety Monitoring (DSM) Plans at Memorial Sloan-Kettering Cancer Center were approved by the National Cancer Institute in September 2001. The plans address the new policies set forth by the NCI in the document entitled "Policy of the National Cancer Institute for Data and Safety Monitoring of Clinical Trials" which can be found at: <http://cancertrials.nci.nih.gov/researchers/dsm/index.html>. The DSM Plans at MSKCC were established and are monitored by the Clinical Research Administration. The MSKCC Data and Safety Monitoring Plans can be found on the MSKCC Intranet at: <https://one.mskcc.org/sites/pub/clinresearch/Documents/MSKCC%20Data%20and%20Safety%20Monitoring%20Plans.pdf>.

There are several different mechanisms by which clinical trials are monitored for data, safety and quality. There are institutional processes in place for quality

assurance (e.g., protocol monitoring, compliance and data verification audits, the therapeutic response, and staff education on clinical research QA) and departmental procedures for quality control, plus there are two institutional committees that are responsible for monitoring the activities of our clinical trials programs. The committees: Data and Safety Monitoring Committee (DSMC) for Phase I and II clinical trials, and the Data and Safety Monitoring Board (DSMB) for Phase III clinical trials, report to the Center's Research Council and Institutional Review Board.

During the protocol development and review process, each protocol will be assessed for its level of risk and degree of monitoring required. Every type of protocol (e.g., NIH sponsored, in-house sponsored, industrial sponsored, NCI cooperative group, etc.) will be addressed and the monitoring procedures will be established at the time of protocol activation.

17.0 PROTECTION OF HUMAN SUBJECTS

Risks of Study Participation: Patients who will undergo a treatment that deviates from the current standard of care for their disease will be those patients in Cohort 2 who receive a dose of radiation of 30Gy to the surgical bed and lymph nodes, a neck dissection at three to four months post-chemoradiation, and a possible booster dose of chemoradiation following neck dissection (this booster dose is dependent on the result of the planned neck dissection). The risks involved include those entailed by giving a decreased dose of radiation and a neck dissection at three to four months post-chemoradiation. However, the risk associated with the decreased dose of radiation is mediated by the neck dissection three to four months post-chemoradiation. Should any residual disease be discovered at the time of this neck dissection, the patient will be treated with a chemoradiation boost per standard of care. These patients will be closely monitored throughout their treatment on this protocol, and will receive standard of care treatment should any complications occur.

Financial Costs to Patients: All diagnostic and therapeutic interventions except for the ¹⁸F-FMISO PET/CT scans and the neck dissection three to four months post-chemoradiation for select Cohort 2 patients are part of the current routine care of patients/subjects eligible for this study. A research grant will cover the cost of the ¹⁸F-FMISO -PET scans and the tracer, the optional ¹⁸F-FMISO PET image-guided core biopsies, and the neck dissections. In addition, the multiparametric scans on the Phillips MR machine will not generate a charge. There are no additional financial costs or burden to the patient beyond the charges routinely incurred as part of standard medical care.

Patient Confidentiality: Patient/subject privacy and confidentiality will be maintained according to MSKCC guidelines and all data derived from this study will be kept in a secure database. All data and results will be anonymously reported with regard to individual subjects.

Voluntary nature of the study: Subjects will be made aware of the voluntary nature of the study as part of the informed consent process. They will be allowed to withdraw participation at any time without the risk of alteration in the quality of their medical care.

17.1 Privacy

MSKCC's Privacy Office may allow the use and disclosure of protected health information pursuant to a completed and signed Research Authorization form. The use and disclosure of protected health information will be limited to the individuals described in the Research Authorization form. A Research Authorization form must be completed by the Principal Investigator and approved by the IRB and Privacy Board.

For the biospecimen banking and analysis study, it will be explained that future research may also be done to identify changes in genes that predict risk for cancer or other diseases; if such germline genetic research is performed, then to be in compliance with New York State Law (New York State Civil Rights Law §79-1(30(a)), it will not be possible to provide results of research tests not performed in a New York State Department of Health approved clinical laboratory.

The consent indicates that samples and genetic information collected may be shared with other qualified researchers. Such information will not include identifying information such as name. It is also stated in the consent and Research Authorization that research data (e.g. genomic sequence) may be placed into databases monitored by the National Institutes of Health, and may be made accessible to investigators approved by the U.S. government.

The requirements for submission of genotype/phenotype data into the NIH GWAS Repository (or any other public database) will be outlined in the biospecimen analysis application, i.e., IRB Biospecimen Correlative Protocol/HBUC Application/Application of Exemption for Existing data.

17.2 Serious Adverse Event (SAE) Reporting

Any SAE must be reported to the IRB/PB as soon as possible but no later than 5 calendar days. SAE reporting is required for 30 days after the last ¹⁸F-FMISO PET/CT scan. Any SAEs that occur after the 30 day period and that are at least possibly related to the ¹⁸F-FMISO isotope must be reported. The IRB/PB requires a Clinical Research Database (CRDB) SAE report is submitted electronically to the SAE Office at [contact] containing the following information:

Fields populated from the CRDB:

- Subject's name (generate the report with only initials if it will be sent outside of MSKCC)
- Medical record number
- Disease/histology (if applicable)
- Protocol number and title

Data needing to be entered:

- The date the adverse event occurred
- The adverse event
- Relationship of the adverse event to the treatment (drug, device, or intervention)
- If the AE was expected
- The severity of the AE
- The intervention
- Detailed text that includes the following information:
 - A explanation of how the AE was handled
 - A description of the subject's condition
 - Indication if the subject remains on the study
 - If an amendment will need to be made to the protocol and/or consent form

The Principal Investigator's signature and the date it was signed are required on the completed report.

For IND/IDE protocols:

The CRDB AE report should be completed as above and the FDA assigned IND/IDE number written at the top of the report. If appropriate, the report will be forwarded to the FDA by the SAE staff through the IND Office.

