- 1.16 Perform a FDG PET/CT scan at 3 months (window +/- 4 weeks) post-RT for Cohort 1 patients. Perform a planned neck dissection at three to four months (+/- four weeks) post-RT for Cohort 2 patients who received 30Gy.
- 1.17 Standard of care follow-up.
- 1.18 Longitudinal chart review for adverse event assessment, locoregional control rates, and disease status as assessed through standard of cares through two years post-treatment for Cohort 1 and Cohort 2.

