4.0 OVERVIEW OF STUDY DESIGN AND INTERVENTION

4.1 Design

PROTOCOL SUMMARY

TIMEPOINT	COHORT 1	COHORT 2
Pretreatment	All Patients	All Patients

	
1) Patient simulation. 2) FDG scan with immobilization. 3) Recommended pretreatment MR scan with immobilization when possible (unless contraindicated, for main campus only). 4) ¹⁸F-FMISO scan (only 1 injection). Patient injected on the PET scanner: (a) Dynamic scan from 0-45 min (b) 10 min scan at about 90 min (c) 10 min scan at about 150-180 min 5) ¹⁸F-FMISO image-guided core biopsy (optional, if consented)
	
1) ¹⁸F-FMISO scan (only 1 injection). Patient injected on the PET scanner: (a) Dynamic scan from 0-45 min (b) 10 min scan at about 90 min (c) 10 min scan at about 150-180 min

During Treatment	
Select Patients
 
1) Repeat ¹⁸F-FMISO scan (only 1 injection) that occurs 5-10 treatment days after RT start*. Patient injected on the PET scanner: (a) Dynamic scan from 0-45 min (b) 10 min scan at about 90 min (c) 10 min scan at about 150-180 min 2) ¹⁸F-FMISO image-guided core biopsy (optional, if consented) 3) Recommended approximately weekly MRI when possible (unless contraindicated, for main campus only). Recommended DCE-MRI between treatment weeks one and two and between treatment weeks three and four, when possible.
	
Patients who Receive Radiation
 
1) Repeat ¹⁸F-FMISO scan (only 1 injection) that occurs 5-10 treatment days after RT start*. Patient injected on the PET scanner: (a) Dynamic scan from 0-45 min (b) 10 min scan at about 90 min (c) 10 min scan at about 150-180 min

Post-treatment	
All Patients
 
1) Recommended MR Scans at 3, 6, and 12 months (+/- 4 weeks) post end of RT (unless contraindicated, for main campus only) 2) Longitudinal chart review for two years post RT for adverse event assessment and disease status
	
Patients Who Receive 30Gy
 
1) Neck dissection three to four months post-chemoradiation (+/- 4 weeks). (a) If no residual disease, standard of care (b) If residual disease, booster dose of chemoradiation 2) Standard of care

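### The general SAE reporting duty in 17.2 ends 30 days after the last FMISO scan, at least 26 to 31 days before any Cohort 2 planned neck dissection can take place

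*Combined protocol and SAP*

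**What the plan says.** Section 17.2 opens with a general deadline: "Any SAE must be reported to the IRB/PB as soon as possible but no later than 5 calendar days". The next sentence sets the period: "SAE reporting is required for 30 days after the last" FMISO PET/CT scan. The third covers what comes later, and only in part: "Any SAEs that occur after the 30 day period and that are at least possibly related to the" FMISO isotope are still to be reported. The report form in the same section has a field for "Relationship of the adverse event to the treatment (drug, device, or intervention").

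The timing of the Cohort 2 steps is given elsewhere:

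- **Last scan.** The design table in 4.1 places, in its during-treatment row, a repeat FMISO "scan (only 1 injection) that occurs 5-10 treatment days after RT start". Sections 3.0 and 9.0 agree on this timing. Section 5.0 allows at most two FMISO injections per patient, so no later scan is planned.
- **Dissection.** Schema item 1.16: "Perform a planned neck dissection at three to four months (+/- four weeks) post-RT for Cohort 2 patients who received 30Gy". The 4.1 table runs the clock from chemoradiation instead: "Neck dissection three to four months post-chemoradiation (+/- 4 weeks").
- **Booster.** Sections 4.1 and 17.0 place any booster chemoradiation after the dissection, when residual disease is found.

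Section 17.0 identifies where the trial departs from usual care: "Patients who will undergo a treatment that deviates from the current standard of care for their disease will be those patients in Cohort 2". It means those given 30 Gy, the dissection and possibly the booster. Section 11.0 lists rare but serious risks of the dissection, including hematoma needing reoperation, nerve injury and chyle leak.

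**The concern.** The reporting window follows the tracer, from which section 11.0 expects no side effects. It does not follow the intervention that section 17.0 calls non-standard. Read as written, a serious bleed, a chyle leak or a death after the dissection carries no 5-day IRB reporting duty under 17.2 unless the isotope may be implicated.

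This matters because section 17.0 presents the dissection as the safeguard for the reduced dose, and because a research grant, not routine care, pays for it. Harm from the safeguard is what an IRB would need to hear about quickly. There is also a mismatch with section 14.0, which counts any death within 4 months of the end of radiotherapy as a Cohort 2 failure. Such a death can count against the feasibility endpoint without being promptly reportable.

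**Working it through.** The plan gives no figure for this interval, so there is none to reproduce. The check is date arithmetic, counted from the end of radiotherapy (RT) as day 0.

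**Inputs**

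- General SAE window: 30 days after the last FMISO scan (17.2).
- Last scan: treatment days 5 to 10 of RT, so no later than day 0 (3.0, 4.1, 9.0).
- Dissection: 3 to 4 months after RT, ± 28 days (schema 1.16).
- Failure period: 4 months from the end of RT (14.0).
- Length of a month: not defined. Across calendar start dates, 3 months last 89 to 92 days and 4 months last 120 to 123. The alternative readings are 12 weeks (84 days) and 16 weeks (112 days).

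**Minimum gap**

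Latest closure of the window = 0 + 30 = day 30.

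Gap = (3 months − 28) − 30.

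| Reading of 3 months | Earliest dissection | Gap beyond the window |
|---|---|---|
| 89 days (shortest calendar) | 89 − 28 = day 61 | 61 − 30 = 31 days |
| 92 days (longest calendar) | 92 − 28 = day 64 | 64 − 30 = 34 days |
| 12 weeks | 84 − 28 = day 56 | 56 − 30 = 26 days |

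These are lower bounds, because they put the scan on the last day of RT. For the window to reach the earliest dissection, the scan would have to take place at least 31 days (26 on the 12-week reading) after RT ended, which the scan rule excludes. Running the clock from the end of chemoradiation, as 4.1 does, cannot shorten the gap, since chemoradiation does not end before RT does.

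**Effect of an earlier scan.** The documents give no fraction count for 30 Gy. Assuming five fractions a week, the minimum gap in days (calendar months / 12 weeks) is:

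| Assumed fractions | Scan on treatment day 10 | Scan on treatment day 5 |
|---|---|---|
| 10 | 31 / 26 | 38 / 33 |
| 12 | 33 / 28 | 40 / 35 |
| 15 | 38 / 33 | 45 / 40 |
| 17 | 40 / 35 | 47 / 42 |

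If the last scan were the pre-surgical one, the gap would be larger still.

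**Latest permitted dissection.** 4 months + 28 days = 120 + 28 = 148 to 123 + 28 = 151 days after RT, or 112 + 28 = 140 days at 16 weeks.

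**Share of the failure period outside the general duty (minimum).** 120 − 30 = 90 of 120 days (75%); 123 − 30 = 93 of 123 (76%); at 16 weeks, 112 − 30 = 82 of 112 (73%).

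**Whether another section supplies the duty**

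- Section 11.0's reporting sentence covers only reactions to a radiopharmaceutical.
- Schema item 1.18 provides chart review for two years, with no deadline and no report to the IRB.
- Section 17.0 promises close monitoring of these patients but sets no reporting rule.
- Sections 16.1 and 16.2 point to institutional monitoring plans that are not in the documents.

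**The case against.** The first sentence of 17.2 has no time limit, the form's relationship field would include surgery, and the word only does not appear in the section. An investigator could therefore report a dissection event under the first sentence alone. That reading is possible, but it leaves the next two sentences with nothing to do: a 30-day period and a residual duty for isotope-related events have no purpose if every SAE is reportable indefinitely. The restrictive reading is the natural one.

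Other points on that side carry some weight:

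- **Booster.** Section 17.0 also calls the boost standard of care, and 4.2 and 9.0 describe it as further standard chemoradiation. The booster part is therefore weaker, and the case rests mainly on the dissection.
- **Unseen plans.** An institutional monitoring plan may already require prompt reporting. The protocol text shows a gap in the stated duty. It does not show that events went unreported.
- **Other safeguards.** Two-year chart review and removal for unacceptable toxicity (13.0) remain, so the endpoint data are not impaired. The overlap with the 4-month failure period illustrates the mismatch and has no analytic consequence.
- **Forward effect.** Section 3.0 says accrual to Cohort 2 was closed at patient 19. The affected patients are the subset of those 19 who received 30 Gy, a number the documents do not give. The amendment may have few patients left to govern, or none.

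None of these supplies the missing duty. They limit how much follows from its absence.

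**Conclusion.** The concern holds. As written, 17.2 places no prompt IRB reporting duty on serious events of the planned neck dissection, or of any booster after it, unless they may be isotope-related. No permitted schedule brings the dissection inside the 30-day window: it misses by at least 31 days in calendar months, or 26 days on a 12-week reading. About three quarters or more of the 4-month failure period carries only the isotope clause.

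The conclusion rests on two things: reading the three sentences of 17.2 together, and the last scan falling no later than the end of RT. It needs no assumption about fractionation. It is limited to the protocol text and to promptness of reporting, and it should be fixed.

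**What to change.** Reconcile 17.2 with 17.0 in one added paragraph, limited to Cohort 2 patients who receive 30 Gy:

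- State that SAE reporting also covers the neck dissection and any booster chemoradiation, for example until 30 days after the later of the two. Thirty days is the length 17.2 already uses after a scan.
- Extend the late-relatedness clause for these patients from the isotope alone to the isotope, the protocol-directed radiation and the dissection.
- If an institutional monitoring plan already requires this, cite it in 17.2 instead.

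The cost is a short amendment and a few more SAE reports from a subset of at most 19 patients. No new visits are needed, since charts are already reviewed for two years. If no dissections or boosters are outstanding, the amendment has no forward effect. In that case, check the existing chart-review records once for serious events after dissection and report any found. The change leaves dose, timing and clinical management as they are.

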17.3 Inclusion of Children in Research

This protocol/project does not include children because the number of children is limited. This statement is based on exclusion 4b of the NIH Policy and Guidelines on the Inclusion of Children as Participants in Research Involving Human Subjects.

18.0 INFORMED CONSENT PROCEDURES

Before protocol-specified procedures are carried out, consenting professionals will explain full details of the protocol and study procedures as well as the risks involved to participants prior to their inclusion in the study. Participants will also be informed that they are free to withdraw from the study at any time. All participants must sign an IRB/PB-approved consent form indicating their consent to participate. This consent form meets the requirements of the Code of Federal Regulations and the Institutional Review Board/Privacy Board of this Center. The consent form will include the following:

1. The nature and objectives, potential risks and benefits of the intended study.
2. The length of study and the likely follow-up required.
3. Alternatives to the proposed study. (This will include available standard and investigational therapies. In addition, patients will be offered an option of supportive care for therapeutic studies.)
4. The name of the investigator(s) responsible for the protocol.

5. The right of the participant to accept or refuse study interventions/interactions and to withdraw from participation at any time.

Before any protocol-specific procedures can be carried out, the consenting professional will fully explain the aspects of patient privacy concerning research specific information. In addition to signing the IRB Informed Consent, all patients must agree to the Research Authorization component of the informed consent form.

Each participant and consenting professional will sign the consent form. The participant must receive a copy of the signed informed consent form.

20.0 APPENDICES

Not applicable.
